5. RECRUITMENT METHODS

5.1 INCLUSION AND EXCLUSION CRITERIA

Eligible participants will be recruited using electronic medical records from Northwestern Medicine Enterprise Data Warehouse (NMEDW) using the below inclusion/exclusion criteria for search criteria. No special populations will be targeted for the enrollment in this study. Additional patient referrals will be made by the physicians who are participating as investigators on this study. The referring physicians of patients to the study will make an assessment if a potential study subject can provide informed consent and will not refer patients unlikely to understand what is being asked of them. All potential subjects will be evaluated by research staff to match them to the inclusion and exclusion criteria that has been established.

5.1.1 Inclusion Criteria

1. ≥22 years old
2. Subjects with suspected OSA based on history and physical. Subjects with self-reported symptoms of OSA based on the STOP-Bang questionnaire indicating affirmative answers to any of the following: snoring, daytime fatigue/sleepiness/tiredness, partners who have observed the subject stopping breathing or choking/gasping during sleep. Persons with a previous diagnosis of OSA are also eligible.
3. Willingness to give written consent and comply with study procedures

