4.1 Primary Outcome Measures

- Analysis of variation between nights of AHI derived from ANNE Sleep system across multiple sleep nights at home
- Analysis of agreement for diagnosis of moderate to severe OSA by determining a patient's Apnea-Hypopnea Index (AHI) wearing the ANNE Sleep system and WatchPAT ONE over one (1) night worn concurrently
- Patient responses on psychometric surveys for comfort and usability comparing ANNE Sleep and WatchPAT ONE

•

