5.1.2 Exclusion Criteria

- 1) An unstable medical condition, acute or chronic, that in the opinion of the investigator puts the subject at health risks related to this trial or interferes with the clinical trial and data collection based on the opinion of the investigator, this includes but is not limited to:
 - A. Significant cardiorespiratory disease: patients that are oxygen dependent, previous hospitalization for cardiorespiratory issues, or left ventricular ejection fraction \leq to 40%
 - B. Respiratory muscle weakness due to a neuromuscular condition
 - C. Awake hypoventilation or suspicion of sleep related hypoventilation
 - D. Chronic opioid medication use
 - E. History of stroke
 - F. History of severe insomnia
- 2) Inability to understand instructions
- 3) Has a skin abnormality that precludes assessment
- 4) Has a history of dementia
- 5) Patients with implanted pacemakers or defibrillators

STU#: STU00214445

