8.1.2 Initial Visit Day: Screening/Enrollment

The subject will have the option to discuss with the study coordinator over the phone or by a Zoom teleconference from the subject's personal device. If Zoom communication is selected a unique meeting number and password known only to the subject will be provided. The study coordinator will monitor the number of attendees in the meeting and restrict meetings to IRB approved researchers on this study, the study subject, and additional people at the subject's discretion. Researchers will host the Zoom sessions and will utilize the waiting room feature to ensure that only the appropriate participants are included on the call.

The study coordinator will cover following topics associated with the study during the Screening/Enrollment visit:

STU#: STU00214445

- (1) Informed Consent will be reviewed and signed electronically using REDCap.
- (2) The qualified subject will be asked to schedule a study date to participate at home. The nights of sensor wear do not need to be consecutive. Subjects will be instructed to set-up both devices on Night One of sleep testing and then only the ANNE device on Nights 2-4.
One Night = HST and ANNE Sleep
3 Additional Nights = ANNE Sleep only
The target time frame will be to complete the sleep nights within 8 weeks of enrollment.
- (3) Subjects will be advised to avoid alcohol and sleep medication use such as antihistamine (OTC) or prescribed medicines for sleep support on the testing night. Any use of these substances on the night of monitoring sleep will be asked to be recorded in the diary.
- (4) Subjects will be informed how to complete the Demographic, Medical History and Sleep Survey sleep diary and usability survey (**Appendix A-C**). The surveys should be available to complete via an email link through REDCap or printed out forms.

Any subject's questions or concerns associated with the study will also be addressed.

At least 24 hours prior to the subject's sleep nights, the study coordinator will contact the participant by phone to confirm their planned sleep study nights at home.

The below sections describe the procedures for setting up the ANNE and HST devices, respectively.

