| If you selected any of the above disorders, please include dates of diagnosis and current status (ongoing or resolved). If resolved, please include end date: | |

STU#: STU00214445

| | |
|---|---|
| Are you currently diagnosed or do you have a history of any psychiatric or psychological disorders? | |
| Please select all that apply: | 1, Bipolar disorders 2, Depression 3, Anxiety 4, Post-traumatic stress disorder (PTSD) 5, Schizophrenia 6, Personality disorders 10, Other |
| If other, please explain: | |
| If you selected any of the above disorders, please include dates of diagnosis and current status (ongoing or resolved). If resolved, please include end date: | |
| Are you currently diagnosed or do you have a history of any lymphatic or hematologic disorders? | |
| Please select all that apply: | 1, Lymphedema 2, Hodgkin's Lymphoma 3, Non-Hodgkin's Lymphoma 4, Anemia 5, Sickle cell 6, Leukemia 10, Other |
| If other, please explain: | |
| If you selected any of the above disorders, please include dates of diagnosis and current status (ongoing or resolved). If resolved, please include end date: | |
| Are you currently diagnosed or do you have a history of any skin or dermatological disorders? | |
| Please select all that apply: | 1, Acne 2, Hives 3, Rosacea 4, Eczema 5, Psoriasis 6, Melanoma 10, Other |
| If other, please explain: | |
| If you selected any of the above disorders, please include dates of diagnosis and current status (ongoing or resolved). If resolved, please include end date: | |
| Are you currently diagnosed or do you have a history of any musculoskeletal disorders? | |
| Please select all that apply: | 1, Carpal tunnel 2, Arthritis 3, Osteoporosis 4, Tension Neck Syndrome 5, Tendonitis 6, Broken bone 7, Tendon or Ligament Sprain 8, Torn Rotator Cuff 9, Ruptured or Herniated Disc 10, Other |
| If other, please explain: | |
| If you selected any of the above disorders, please include dates of diagnosis and current status (ongoing or resolved). If resolved, please include end date: | |
| Do you have a history of any allergies? This can include seasonal, skin, food, or drug/medicine allergies. | |
| Please list allergies here, including start dates and current status (ongoing or resolved). If resolved, please include end date: | |
| Do you have a history of any other medical illness? | |

STU#: STU00214445

| | |
|---|---|
| SLEEP DIARY | |
| The following questions are about your sleep last night (before study visit). | |

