| Please list all other medical illnesses here, including start dates and current status (ongoing or resolved). If resolved, please include end date: | |
| 2. Did you wear CPAP Device last night? | |
| If yes, level of titration: | |
| 3. What time did you go into bed? {time_in_bed} | |
| 4. What time did you try to go to sleep? {time_sleep} {ampm} | |
| | 1, AM 2, PM |
| 5. How long did it take you to fall asleep? | |
| 6a. How many times did you wake up, not counting your final awakening? | |
| 6b. In total, how long did these awakenings last? | |
| 7a. What time was your final awakening? | |
| 7b. After your final awakening, how long did you spend in bed trying to fall back asleep? | |
| 7c. Did you wake up earlier than you planned? | |
| 7d. If yes, how much earlier? | |
| 8. What time did you get out of bed for the day? {time_up} {am_and_pm} | |
| 9. In total, how long did you sleep? | |
| 10. How would you rate the quality of your sleep? | 1, Very poor 2, Poor 3, Fair 4, Good 5, Very good |
| 11. How rested or refreshed did you feel when you woke up for the day? | 1, Not at all rested 2, Slightly rested 3, Somewhat rested 4, Well-rested 5, Very well-rested |
| 12a. How many times did you nap or doze? | |
| 12b. In total, how long did you nap or doze? | |
| 13a. How many drinks containing alcohol did you have? | |
| 13b. What time was your last drink? {time_drink}{am_pm_2} | |
| 14a. How many caffeinated drinks (coffee, tea, soda, energy drinks) did you have? | |
| 14b. What time was your last drink? {time_coffee}{am_pm_3} | |
| 15. Did you take any over-the-counter or prescription medication(s) to help you sleep? | |
| Type of medication: | |
| Dose: | |
| Time taken: | |

STU#: STU00214445

| | |
|--|--|
| Did you take any additional medications? | |
| Type of medication: | |
| Dose: | |
| Time taken: | |
| 16. Comments, if applicable: | |

STU#: STU00214445

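### PAP use is not clearly recorded for each test night although previously diagnosed subjects are eligible, so a mix of PAP and non-PAP nights could be reported as between-night AHI variation

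*Combined protocol and SAP*

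**What the plan says.** **Eligibility.** Section 5.1.1 admits treated and untreated subjects alike: "Persons with a previous diagnosis of OSA are also eligible". Section 5.1.2 and the screening questions in Appendix F do not mention PAP. The nearest medication item is "D. Chronic opioid medication use".

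**Nights.** Section 8.1.2 plans one night with both devices, then "3 Additional Nights = ANNE Sleep only". It adds that "The nights of sensor wear do not need to be consecutive"; the target is to finish within 8 weeks of enrollment.

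**Outcome.** The first primary outcome in Section 4.1 is "Analysis of variation between nights of AHI derived from ANNE Sleep system across multiple sleep nights at home".

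**What is recorded.** The schedule of events marks a sleep diary for Night One and for Nights Two to Four, and places demographics and medical history at screening. Appendix A, the form titled as the sleep diary, has items on alcohol (12a-b) and sleep aids (14a-b) and none on PAP. The only CPAP item is in the diary section of Appendix C: "Did you wear CPAP Device last night". That section is introduced by "The following questions are about your sleep last night (before study visit". On alcohol and sleep medication, Section 8.1.2 advises subjects to avoid them and adds: "Any use of these substances on the night of monitoring sleep will be asked to be recorded in the diary".

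**Analysis.** Section 10.2 summarizes the four-night AHIs descriptively, by diagnosis. Section 10.3 lists the diary among exploratory descriptive material. Neither gives a rule for nights with PAP, alcohol or a sleep aid.

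**The concern.** A study of night-to-night variation needs to know which conditions changed between nights. PAP is the obvious one in a sample that may include treated patients, and the sponsor evidently expects some, since Appendix C asks about CPAP and its titration level. That question is tied to a night before the study visit, while the form that appears to serve the test nights omits it.

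The nights may be spread over weeks, so a subject could wear PAP on some and not on others. The resulting shift in AHI would then be counted as natural or device variability. The recording itself offers no check: the signals in Table 1 of the ANNE Sleep Scoring Manual (Section 2.3) include neither airflow nor mask pressure. With about 30 completers, a few such subjects could carry weight.

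Alcohol and sleep aids raise a lesser matter. The information exists, but nothing in the plan connects it to the AHI of the same night.

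**Working it through.** **1. Which form covers which night?**

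| Place | What it implies |
|---|---|
| Schedule of events | Diary on all four test nights; none at screening |
| Appendix A | Titled as the sleep diary; no PAP item |
| Appendix C, diary section | CPAP item, for the night before the study visit |
| Section 8.1.2, item 4 | Refers to Appendices A to C together |
| Section 8.2, item 1 | Gives Appendix C after data collection |

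The most natural reading is that Appendix A is the nightly diary and that Appendix C, mostly demographics and history, belongs to screening. The last two rows do not settle this. A single administration of Appendix C covers at most one night.

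**2. Possible size.** The documents give no within-subject SD, no AHI shift under PAP and no frequency of mixed use, and there is no stated figure to reproduce. What follows is illustration only. The pooled within-subject SD serves as the summary; Section 10.2 does not name a specific one.

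Let s be the true within-subject SD, D the shift on a PAP night, m the number of shifted nights out of 4, and f the fraction of subjects affected. Then

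expected pooled variance = s² + f × D² × m(4 − m)/12.

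For m = 1 the added term is f × D²/4. For m = 0 or m = 4 it is zero. With 30 subjects and m = 1:

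| s | D | Subjects | Added variance | Pooled SD | Change |
|---|---|---|---|---|---|
| any | any | 0 | 0 | s | 0% |
| 6 | 20 | 3 | (3/30) × 100 = 10 | √46 = 6.78 | +13% |
| 6 | 27 | 5 | (5/30) × 182.25 = 30.4 | √66.4 = 8.15 | +36% |
| 8 | 15 | 2 | (2/30) × 56.25 = 3.75 | √67.75 = 8.23 | +3% |
| 4 | 27 | 8 | (8/30) × 182.25 = 48.6 | √64.6 = 8.04 | +101% |

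A simulation of one further case (s = 5, D = 20, f = 20%) gave 6.70, against 6.71 from the formula.

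**3. Against sampling error.** Thirty subjects with four nights give 30 × 3 = 90 degrees of freedom, so the 95% confidence interval for a within-subject SD runs from 0.87 to 1.17 times the estimate. An inflation of 13% lies within that margin and one of 36% lies beyond it.

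**The case against.** The strongest reply is that no section assigns Appendix A to the test nights. The diary in Appendix C repeats nearly the same items and adds CPAP; if it were the form used each night, PAP would be captured. This stands as a reason to call the documents unclear and to ask for reconciliation. It does not remove the gap, because the wording of Appendix C and the screening place of its demographic and history content point the other way.

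A second reply is that mixed PAP use is an inference. That is right: the documents never say that subjects will wear PAP on test nights. They do not rule it out either.

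Three stronger readings are tempting, and the documents do not support them.

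- A reader might infer that the problem is beyond repair. Appendix C records a confirmed sleep apnea diagnosis with dates and status, so the analysis could be repeated without previously diagnosed subjects. The follow-up call or the diary's comment field might also catch some cases. These remedies are cruder or unsystematic, but they exist.
- A reader might infer that a PAP night counts as a missed diagnosis. The agreement outcome uses Night One, when both devices record the same conditions. Nights Two to Four have no comparator, and the plan defines no missed diagnosis.
- A reader might infer that alcohol and sleep-aid nights go unmarked. They are recorded and can be found later; only a prespecified use of the record is missing.

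**Conclusion.** The point holds as a gap in recording and prespecification. Followed on its most natural reading, the plan could report a mix of PAP and non-PAP nights as between-night AHI variation, with no reliable way to identify the nights afterwards. Only a coarser analysis without previously diagnosed subjects would remain.

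The effect is zero if no subject mixes nights. Under the central assumptions above it is a 13% to 36% rise in the pooled within-subject SD, and every input to that range is assumed. PAP on all four nights would add no between-night shift, though it could lower the AHI level and change the severity mix. None of the arithmetic bears on alcohol or sleep aids, where the omission is a modest one of analysis. The change is worth making because it is cheap and PAP use is best recorded at the time.

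**What to change.** 1. Put the existing Appendix C CPAP question into the diary used on each of the four test nights.
2. Reconcile Sections 8.1.2 and 8.2, the schedule of events, and Appendices A and C, so that it is clear which form is completed for which night.
3. In Section 10.2, present between-night AHI variation and severity classification with PAP-flagged nights shown separately.
4. Add a sensitivity table that omits nights on which the diary records alcohol or a sleep aid.

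The cost is one diary item, the split presentation and one extra table, plus fewer nights in the restricted analysis. No position is taken on whether PAP should be used on test nights, and no change to anyone's treatment is implied.

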5.1.2 Exclusion Criteria

- 1) An unstable medical condition, acute or chronic, that in the opinion of the investigator puts the subject at health risks related to this trial or interferes with the clinical trial and data collection based on the opinion of the investigator, this includes but is not limited to:
 - A. Significant cardiorespiratory disease: patients that are oxygen dependent, previous hospitalization for cardiorespiratory issues, or left ventricular ejection fraction \leq to 40%
 - B. Respiratory muscle weakness due to a neuromuscular condition
 - C. Awake hypoventilation or suspicion of sleep related hypoventilation
 - D. Chronic opioid medication use
 - E. History of stroke
 - F. History of severe insomnia
- 2) Inability to understand instructions
- 3) Has a skin abnormality that precludes assessment
- 4) Has a history of dementia
- 5) Patients with implanted pacemakers or defibrillators

STU#: STU00214445

5.2 RECRUITMENT METHODS

Identifying potential participants will be through the Electronic Data Warehouse (EDW) and through the use of study flyers and recruitment materials. The EDW at Northwestern is updated daily. An algorithm can be set up based on the eligibility criteria of the trial to identify potential participants that have met enrollment criteria. Data gathered in the EDW request will include Name, contact information (address, email and/or phone), Date of Birth, MRN, hospitalization date(s), and if applicable, date that a HST or PSGG is ordered. The EDW request may exclude people based on the exclusion criteria. The use of the EDW will be used exclusively for recruitment purposes and no data from the warehouse will be added to the study data set for research analysis. The use of study flyers or advertisements will also be shared with potential study subjects who will be given contact information to follow up with the study team.

6. STUDY INVESTIGATIONAL DEVICE:

ANNE™ Sleep system

Sibel's ANNE™ Sleep system includes two skin-mounted, bio-integrated sensors to record vital signs, a wireless charger, a wireless charger adaptor, single-use chest adhesives, single-use finger adhesives, and a mobile device with a mobile software application that enables data recording for download for further analysis.

Heart rate (HR), snore, chest movement, and body position are recorded from the ANNE™ Chest sensor. Blood oxygenation (SpO₂), peripheral arterial tonometry (PAT), and pulse rate are recorded from the ANNE™ Limb sensor. PAT is indicative of vasoconstriction, which can serve as a proxy for respiratory disturbances and accepted by the American Academy of Sleep Medicine for use as a component of home sleep testing.

The first sensor (chest unit) located on the chest contains a 3-axis gyroscope and 3-axis accelerometer, Bluetooth Low Energy System-on-Chip (SoC), a Lithium-Polymer battery, power management component, an analog front-end component, passive electrodes for electrocardiogram (ECG).

The second sensor (limb unit) located on the finger of a patient contains Bluetooth Low Energy SoC, a Lithium-Polymer battery, power management solution, low-power microcontroller, an analog front-end component, pulse oximeter (SpO₂).

The chest sensor is placed on the body via a single-use chest adhesive. Both adhesives will be removed and discarded after one use. The limb sensor is held in place by a single-use finger adhesive, which is removed and discarded after one use, then replaced with a new finger adhesive.

Chest Unit

Limb Unit

STU#: STU00214445

Multi-Use

Figure 1. The ANNE™ Sleep consists of 2 sensors, a chest unit worn on the thorax and a limb unit that folds over the index finger.

6. PREPARATION OF ANNE™ SLEEP SYSTEM

6.1 Standard study supply kit

The study sponsor company will ship ANNE™ Sleep system (study supply kit) to Northwestern.

| Study supply kit list |
|---|
| 
● Cardboard mailer box● Wearable study sensors● Study devices (Tablet(s) or smart phone(s) with sensor application pre-loaded).● Wireless charger(s), charger adaptors● Device accessories; chest adhesives, finger adhesives● Printed instructions or other study materials |

The research coordinator from the sponsor will document tracking records of each device. All adhesives are single use with new ones provided to each new subject.

6.2 Study Kit Cleaning

Participants will return study supply kits in person by meeting a member of the research team or by mailing them back using pre-paid shipping labels. Study sensors are reusable after completion of study procedures and data collection.

The detailed sanitation instructions for the study kit are attached as **APPENDIX D**.

7. PREPARATION OF WatchPAT ONE

The WatchPAT ONE is a commercialized HST system, which received FDA 510(k) clearance (KK183559). The WatchPAT ONE will be prepared by following its operation manual.

The study coordinator will provide study participants a case with everything needed for a WatchPAT ONE. The case will include:

STU#: STU00214445

- An WatchPAT ONE device. This is a rectangular device that will keep track of body position (information such as whether a person is lying on their back, side, or stomach). It will also store all the information from the system.
- A pulse oximeter. This is a wire with a gray rubber sensor placed on the finger. It will measure pulse, blood flow, and the amount of oxygen in the blood. The pulse oximeter should already be attached to the device.
- A chest sensor. The Chest Sensor monitors snoring, movement, and body position. The chest sensor should already be attached to WatchPAT ONE.
- AA batteries. This will only use these if the batteries inside the HST device stop working.

8. STUDY PROCEDURES

8.1 Sleep Study Procedures

8.1.1 Consent form

To protect participant confidentiality, we will conduct all research-related discussions and informed consent procedures in a private setting. The consent process will be completed either in person or remotely by using an electronic consent document and collection of an electronic signature with REDCap or other electronic signature service like Adobe DocuSign. The study coordinator will review the Informed Consent in person, by phone or in Zoom during the remote informed consent discussion.

The study procedures, risks, and benefits will be discussed and the study team will answer all questions prior to obtaining consent. The person performing the Informed Consent process, will ask questions of the study subject to confirm understanding and comprehension of the study. All versions of the consent forms will be approved by the relevant ethics committees prior to study initiation.

Eligible participants who do not wish to participate in this study will continue to receive care according to local clinical standards.

Informed Consent will be reviewed and signed electronically using REDCap.

